Which of the following describes your current situation? (You can select more than one answer)

TOGGLE of 10 choices

[Require ≥ 1 choices]

- 1 In paid employment or self-employed
- 2 Retired -> GO TO D12
- 3 Looking after home and/or family
- 4 Unable to work because of sickness or disability
- 5 Unemployed -> GO TO D12
- 8 On paid leave (furlough)
- 6 Doing unpaid or voluntary work
- 7 Full or part-time student
- 7 None of the above [EXCLUSIVE]
- 3 Prefer not to answer [EXCLUSIVE]

If more than one situation applies, select all that are appropriate.

[D9AA (UKB)]

How many years have you worked in your current role? (If you have more than one job please answer this, and the following questions on work, for your MAIN role only. Looking after home and/or family should be considered as a job/work)

Enter INTEGER

[Require $\geq 1, \leq$ Current age,

Units: years]

OR

-10 Less than a year

OR

-1 Do not know

OR

-3 Prefer not to answer

If you have more than one 'current job' then answer this question for your MAIN job only (ie: the job that you spend most of your time doing).

If you have been with the same employer, but have changed jobs whilst you have worked for them, then only give the number of years that you have been in your current job (not the number of years that you have been employed by the same company).

For instance, if you have worked as mail-room sorter but then been promoted to manager of the mail-room, please give the number of years you have worked as the mail-room manager only.

If you have changed employers, but have had the same job, please give the total number of years that you have worked in that job. For instance, if you have worked as a cleaner for 3 different companies, please give the total number of years working as a cleaner.

[D9A (UKB)]

In a typical WEEK, how many hours do you spend at work? (Do not include hours travelling to and from work)

Enter INTEGER

[Require ≤ 168 ,

Units: hours]

OR

-1 Do not know

OR

-3 Prefer not to answer

If you have more than one 'current job' then answer this question for your MAIN job only.

Please round up or down to the nearest hour.

[D9G (UKB)]

How many times a WEEK do you travel from home to your main work? (count outward journeys only)

Enter INTEGER

[Require $\geq 0, \leq 999$,

Units: times]

OR

-10 Less than once a week

OR

-1 Do not know

OR

-3 Prefer not to answer

If the number of times varies each week, take an average over the last 4 weeks.

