If you only work from home please enter 0.

[D9E (UKB)]

What types of transport do you use to get to and from work? (You can select more than one answer)

TOGGLE of 6 choices

[Require ≥1 choices]

- 1 Car/motor vehicle
- 2 Walk
- 3 Public transport
- 4 Cycle
- 7 None of the above **[EXCLUSIVE]**
- 3 Prefer not to answer **[EXCLUSIVE]**

If you have more than one 'current job' then answer this question for your MAIN job only.

If you use more than one form of transport then select all that apply.

[D9F (UKB)]

About how many miles is it between your home and your work?

Enter INTEGER

[Require ≥0, ≤ 999,

Units: miles]

OR

-10 Less than one mile

OR

-1 Do not know

OR

-3 Prefer not to answer

If you have more than one 'current job' then answer this question for your MAIN job only.

If you are unsure, please provide an estimate or select 'Do not know'.

If you only work from home please enter 0.

[D9B (UKB)]

Does your work involve walking or standing?

SELECT one of 6 from

- 1 Never/rarely
- 2 Sometimes
- 3 Usually
- 4 Always
- 1 Do not know

-3 Prefer not to answer

If you have more than one 'current job' then answer this question your MAIN job only.

[D9C (UKB)]

Does your work involve heavy manual or very physical work?

- 1 Never/rarely
- SELECT one of 6 from**
- 2 Sometimes
- 3 Usually
- 4 Always
- 1 Do not know
- 3 Prefer not to answer

If you have more than one 'current job' then answer this question for your MAIN job only. Physical work includes work that involves handling of heavy objects and use of heavy tools.

[D9D (UKB)]

Does your work involve shift work?

- SELECT one of 6 from**
- 1 Never/rarely **-> GO TO D12 (UKB)**
- 2 Sometimes
- 3 Usually
- 4 Always
- 1 Do not know
- 3 Prefer not to answer"

Shift work is a work schedule that falls outside of the normal daytime working hours of 9am-5pm. This may involve working afternoons, evenings or nights or rotating through these kinds of shifts.

[D9DA (UKB)]

Does your work involve night shifts?

- SELECT one of 6 from**
- 1 Never/rarely
- 2 Sometimes
- 3 Usually
- 4 Always
- 1 Do not know.
- 3 Prefer not to answer

If you have more than one 'current job' then answer this question for your MAIN job only. Night shifts are a work schedule that involves working through the normal sleeping hours, for instance working through the hours from 12am to 6am.

[D12 (UKB)]

Which of the following qualifications do you have? (You can select more than one)

TOGGLE of 8 choices

[Require ≥ 1 choices]

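### Item D9 accepts several work situations at once, but its unconditional skips can drop working retirees from the work block, while people unable to work are routed into it

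*Protocol*

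**What the plan says.** Appendix E, Section 2 (Work And Education), opens with D9, a ten-choice toggle item on current situation. Its stem allows more than one answer, and its help text repeats the point: "If more than one situation applies, select all that are appropriate". Only the last two choices, none of the above and prefer not to answer, are marked exclusive.

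Two of the eight non-exclusive options carry routing: "Retired -> GO TO D12" and "Unemployed -> GO TO D12". The option "In paid employment or self-employed" carries none, and nothing says which route wins when it is ticked with one of those two. The option "Unable to work because of sickness or disability" carries no routing either; nor do the two exclusive choices.

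The items between D9 and D12 form the work block. They include D9A ("In a typical WEEK, how many hours do you spend at work") and D9D ("Does your work involve shift work"). D9AA tells respondents to count looking after home or family as work, so carers are meant to answer it. There is no similar instruction for people who cannot work.

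**The concern.** The response format and the routing do not fit together. A select-all item can return paid employment and retirement in one record, but the skip is attached to single options as if only one could be chosen. The likeliest people to give that pair are those who work while retired, so the missing work data would be structural and related to age, not random.

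No other item in Appendix E collects working hours, shift work or night work. Section 3.6 says the questionnaire is there to capture factors that linkage can supply only with difficulty or not at all, so a hole here matters.

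The second fault runs the other way. People out of work through illness are asked about the heaviness and shift pattern of a job they do not have. If some choose the lowest category, the unexposed reference group for heavy or shift work contains people already ill, unless the analyst removes them.

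**Working it through.** No power or sample size figure is involved. The check traces the routing as written.

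**1. Items at stake.** Nine items lie between D9 and D12: D9AA (years in role), D9A (hours), D9G (journeys per week), D9E (transport), D9F (distance), D9B (walking or standing), D9C (heavy work), D9D (shift work) and D9DA (night shifts).

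**2. Literal trace.**

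| Ticked at D9 | Route as written |
|---|---|
| Paid employment only | D9AA: work block asked |
| Retired only | D12: block skipped |
| Retired and paid employment | D12: block skipped, all nine items missing |
| Unemployed and paid employment | D12: block skipped, all nine items missing |
| Unable to work only | D9AA: work block asked |
| None of the above, or prefer not to answer | D9AA: work block asked |

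**3. Combinations.** Eight non-exclusive options give 2^8 − 1 = 255 non-empty answers. Those that include paid employment number 2^7 = 128. Of these, the ones with neither retired nor unemployed number 2^5 = 32 and reach the block. The other 128 − 32 = 96 go to D12. These count possible answers, not people.

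**4. The opposite leak, item by item.** D9B, D9C, D9D and D9DA each offer Never/rarely, Sometimes, Usually, Always, Do not know and Prefer not to answer. None offers not applicable. D9A sets only an upper limit of 168, so 0 hours is accepted; D9G and D9F accept 0; D9E has a none-of-the-above choice. At D9D, Never/rarely jumps straight to D12, so a person giving that answer never sees D9DA. The shared code can therefore arise on heavy work and shift work, but not on night shifts.

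**5. Scale.** The protocol gives no figure for how many people would tick both retired or unemployed and paid employment. Purely as an assumption, 0.5% to 3% of the 5 million target would be 0.005 × 5,000,000 = 25,000 to 0.03 × 5,000,000 = 150,000 records. Nothing in the document supports any point in that range.

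**6. Comparison within the questionnaire.** WP4B1 in Section 3 is also multi-select. It states what to do when several options are ticked (show each applicable follow-up in order), and its exits from the block sit only on exclusive choices. D9 has no such rule, and its exits sit on options that can be combined.

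**The case against.** The best defence is that the arrows are shorthand. Y13D, L1 and L5DF are multi-select and give many options their own destination without a precedence rule; taken as single jumps, they would fail for anyone with two conditions. A programmer might therefore let paid employment bring the respondent to D9AA. This stands in part: the outcome for retired plus paid employment is ambiguous, not proven data loss. But paid employment at D9 has no destination of its own to set against the jump, and WP4B1 shows a multiple-response rule written out in full. A specification that depends on the programmer's guess still needs correcting.

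Some stronger readings are tempting, and the document does not support them:

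- **That people unable to work must answer.** They are routed into the block, but can choose Do not know or Prefer not to answer, or enter 0 hours.
- **That the night-work reference group fills with sick people.** The D9D skip prevents that coding.
- **That analyses are necessarily biased, in a known direction.** D9 is itself a questionnaire item, so these respondents can be excluded, and nothing shows how they would answer.
- **That the lost data can never be recovered.** Repeat questionnaires are planned (Section 2.4), consent covers re-contact (Section 3.5), and employment linkage is to be explored (Section 5.2). A later question would, however, reconstruct baseline exposure from memory, and linkage may not hold shift patterns.

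**Conclusion.** The point holds as a routing defect. As written, the unconditional skips on retired and unemployed send anyone who also ticks paid employment past all nine work items. Three other answers that do not indicate work fall through into items that do not fit them.

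The first fault is the more serious: an analyst cannot rebuild a skipped block from the baseline data. The second can be handled in analysis by excluding on D9, at the cost of every user having to know to do so.

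The conclusion rests on reading the arrows literally. On a looser reading the combination rule is simply unstated, and the remedy is the same. The number of participants affected is unknown, and the assumed range above should not be quoted as an estimate. The change is worth making because it is cheap and alters what is collected from a cohort of up to 5 million.

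**What to change.** Remove the two option-level skips and place one rule after D9, using the existing option codes:

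- IF D9 includes 1 (paid employment) or 8 (paid leave), GO TO D9AA;
- ELSE IF D9 includes 3 (home or family) or 6 (unpaid or voluntary work) and does not include 2 (retired), 4 (unable to work) or 5 (unemployed), GO TO D9AA;
- ELSE GO TO D12.

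All 128 combinations with paid employment then reach the block, against 32 now. Retired or unemployed carers and volunteers without paid work or leave continue to skip it. People who tick only unable to work, and those choosing none of the above or prefer not to answer, go to D12.

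A simpler rule that admits anyone ticking 1, 3, 6 or 8 would be worse: it would newly bring retired or unemployed carers and volunteers into the block and lengthen the questionnaire for them.

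The cost is one routing rule in Appendix E. Two small groups who now enter the block would leave it: respondents who tick only student, and carers or volunteers who also tick unable to work, in both cases only where neither paid work nor paid leave is ticked. Students with a job stay in through option 1.

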- 1 College or University degree
- 2 A levels/AS levels/BTEC or equivalent
- 3 O levels/GCSEs or equivalent
- 4 CSEs or equivalent
- 5 NVQ or HND or HNC or equivalent
- 6 Other professional qualifications e.g., nursing, teaching
- 7 None of the above **[EXCLUSIVE]**
- 3 Prefer not to answer **[EXCLUSIVE]**

A levels/AS levels and equivalent includes the Higher School Certificate O levels/GCSEs and equivalent includes the School Certificate. If your education was in another country please choose the category(ies) that best fits with your educational qualifications.

[D11 (UKB)]

At what age did you complete your continuous full-time education?

If you stopped your studies with no intention of returning, please give the age at which you stopped even if you began studying again later in life.

Enter age in years

[Require ≥ 5 , \leq current age,

Expect ≤ 40 ,

Units: years]

OR

0 Still in full time education

OR

-2 Never went to school

OR

-1 Do not know

OR

-3 Prefer not to answer

Please give the age that you completed 'continuous' full time education.

For example, if you stopped your studies when you were 17 years old with the intention that you had completed your studies but then returned to full time studies when you were 24, enter 17.

However if you only temporarily stopped your studies at 17 with the intention that you would return to studies (for instance a gap year) and then completed your full time education at 21, enter 21

[D10 (UKB)]

What is the average total income before tax received by your HOUSEHOLD?

SELECT one of 7 from

- 1 Less than £18,000
- 2 £18,000 to £30,999
- 3 £31,000 to £51,999
- 4 £52,000 to £100,000
- 5 Greater than £100,000
- 1 Do not know
- 3 Prefer not to answer

Add up the incomes of everyone in your household for your answer.

The information you provide is confidential and won't be shared with any tax authorities.

-----**END OF SECTION 2**-----

Your lifestyle [SECTION 3]

Note: square brackets are not seen

Help and hint text is presented in boxes where available

[SECTION INTRO]

In this section we ask you about your day-to-day physical activity.

This will help our researchers look at how exercise is tied to overall health, but also things like how healthy your bones, lungs, and heart as well as diseases such as type 2 diabetes.

We'll also ask about driving habits, sleep patterns and the use of tobacco, vaping and alcohol if relevant.

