Aspects of your lifestyle may have changed during the COVID-19 pandemic. Please answer the questions as accurately as you can based on your current situation.

[WP1 (UKB)]

Thinking about the last 4 weeks, in a typical WEEK, on how many days did you walk for at least 10 minutes at a time?

(Include walking that you do at work, travelling to and from work, and for sport or leisure)

Enter INTEGER

[Require $\geq 0, \leq 7$

Units: days]

OR

-1 Do not know

OR

-2 Unable to walk -> **GO TO WP2**

OR

-3 Prefer not to answer

[WP1A (UKB)]

Thinking about the last 4 weeks, , how many minutes did you usually spend walking on a typical DAY?

Enter INTEGER

[Require $\geq 0, \leq 1440$

Units: minutes]

OR

-1 Do not know

OR

-2 Unable to walk

OR

-3 Prefer not to answer

Count the number of minutes that you usually spend walking in one day.
--

If the time you usually spend walking on each day of the week varies a lot, give an average of the time you spend walking. For instance, if on one day of the week you usually walk for 4 hours but on the other day you walk 2 hours then give the average - that is 3 hours.

[WP2 (UKB)]

Thinking about the last 4 weeks, in a typical WEEK, on how many days did you do 10 minutes or more of moderate physical activities like carrying light loads, cycling at normal pace? (Do not include walking)

Enter INTEGER

[Require $\geq 0, \leq 7$

Units: days]

OR

-1 Do not know

OR

-3 Prefer not to answer

Count the number of days in a week that you do moderate physical activities for at least 10 minutes continuously at a time.

Remember to include activities that you do for work, leisure, travel and around the house.

[WP2A (UKB)]

Thinking about the last 4 weeks, how many minutes did you usually spend doing moderate activities on a typical DAY?

Enter INTEGER

[Require $\geq 0, \leq 1440$

Units: minutes]

OR

-1 Do not know

OR

-2 Unable to walk

OR

-3 Prefer not to answer

If the time you usually spend doing moderate physical activity on each day of the week varies a lot, give an average of the time you spend doing moderate physical activity.

[WP3 (UKB)]

Thinking about the last 4 weeks, in a typical WEEK, how many days did you do 10 minutes or more of vigorous physical activity?

(These are activities that make you sweat or breathe hard such as fast cycling, aerobics, heavy lifting)

Enter INTEGER

[Require $\geq 0, \leq 7$

Units: days]

OR

-1 Do not know

OR

-3 Prefer not to answer

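### The walking-time item (WP1A) is recorded in minutes, but its only worked example ends at 3 hours, so a participant who copies it can enter 3 and be stored as walking 3 minutes instead of 180

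*Protocol*

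**What the plan says.** Protocol, Appendix E, Section 3 (Your lifestyle), item WP1A asks "how many minutes did you usually spend walking on a typical DAY". The specification line takes an integer from 0 to 1440 and gives "Units: minutes". The help text opens with "Count the number of minutes that you usually spend walking in one day". For participants whose walking time varies between days it offers one worked example, built on a 4-hour day and a 2-hour day. That example closes with the instruction "then give the average - that is 3 hours".

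The unit and range line is in square brackets, and the section's own note says "Note: square brackets are not seen". The participant therefore sees the question and the help text, but not the bracketed unit.

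The item just before, WP1, asks "on how many days did you walk for at least 10 minutes at a time". The parallel items for moderate and vigorous activity (WP2A and WP3A) are also in minutes, and neither has an example in hours.

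**The concern.** The question, the first help sentence and the stored unit are all minutes. The only worked example is in hours and stops there. Its closing words tell the participant to give the average, and the figure attached to that instruction is 3. A participant who types 3 is recorded as walking 3 minutes a day.

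Other worked examples in the questionnaire end on a figure in the unit the item collects. Years at current address (D5A1) ends in years, age at leaving education (D11) ends in ages, and time outdoors (WP12A and WP12B) ends in hours for items that ask for hours. WP1A departs from that pattern, so a participant who has learned to copy the example is misled here.

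Any resulting error has a direction. The example concerns walks of 2 to 4 hours a day, so those most likely to follow it are long walkers, and they would land among the least active. Section 3 introduces these items as a means of studying how exercise relates to health and to diseases such as type 2 diabetes. A larger cohort does not average out an error of this kind.

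**Working it through.** **Inputs from Appendix E, WP1A.** Example values of 4 hours and 2 hours; stated answer 3 hours; recorded unit minutes; permitted range 0 to 1440.

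**Step 1. Reproduce the example.** (4 + 2) / 2 = 3 hours. The averaging is correct as stated.

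**Step 2. Convert to the recorded unit.** (240 + 120) / 2 = 180 minutes, or equivalently 3 × 60 = 180.

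**Step 3. Size of the error in one record.** 180 / 3 = 60. A copied 3 is stored 60 times too small.

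**Step 4. Can the stated limit detect it?** 0 ≤ 3 ≤ 1440, so 3 is accepted. A day has 24 hours, so any whole number of hours from 0 to 24 also lies within 0 to 1440. The stated limit cannot separate hours from minutes, and no other check is written for this item.

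**Step 5. Illustration of the effect on the variable.** The documents give neither a distribution of walking time nor an error rate, so both are assumed here. Take true minutes T as lognormal with mean 60 and SD 50:

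- σ² = ln(1 + (50/60)²) = 0.527, so σ = 0.726; μ = ln 60 − σ²/2 = 3.831.
- Share walking 2 hours or more: 1 − Φ((ln 120 − 3.831) / 0.726) = 1 − Φ(1.318) = 9.4%.

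Let a fraction f of that group, and nobody else, enter rounded hours. The affected share of all records is 9.4% × f. The correlations come from a simulation of 4 million records.

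| f among those walking ≥ 2 h | Share of all records affected | Correlation of recorded with true time |
|---|---|---|
| 1% | 0.09% | 0.99 |
| 5% | 0.47% | 0.97 |
| 20% | 1.9% | 0.86 |

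**Step 6. Could the errors be found later?** In the same simulation more than 99% of the hours-for-minutes entries fall below 10. Dropping all records below 10 brings the correlation back to at least 0.99 in all three cases. This does not recover the lost values. It also removes genuine short walkers: under the same distribution about 1.8% of true times are below 10 minutes, from Φ((ln 10 − 3.831) / 0.726).

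**The case against.** The strongest reply is that the unit is stated twice before the example is reached, in the question and in the first help sentence. The example illustrates how to average uneven days and does not say which number to key in, whereas D5A1 and D11 do. The help text may sit behind a HELP button, and the example is addressed only to people whose walking varies a lot. The protocol's section on the baseline questionnaire also reports cognitive testing and a pilot with over 1,500 complete questionnaires. Most of this stands. It makes the error possible rather than certain, and probably uncommon. It does not remove the mismatch, and nothing in the documents shows that this help text in particular was tested.

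A reader might go further in four ways that the documents do not support.

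- **That the error reverses the exposure.** Individual records can move from the top of the scale to the bottom. Even so, correlations of 0.86 to 0.99 describe attenuation, and the variable still ranks people broadly in the right order.
- **That the error would fall on a fixed share of all participants.** Under the illustrative distribution about 28% of people walk less than 30 minutes. Their time would round to 0 hours, and a 4-hour/2-hour example gives them no reason to answer that way. Only long walkers fit the mechanism.
- **That the error could never be found.** The 0 to 1440 limit cannot find it, but an entry below 10 beside a WP1 answer of at least 1 day looks inconsistent. The protocol also foresees data cleaning in general terms (Section 10.2.2).
- **That a weekly walking volume would be wrong by the same factor.** The protocol defines no product of minutes and days.

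**Conclusion.** The example is wrong as written: it is worked in a unit that the item does not collect, and the figure it ends on is a legal entry 60 times too small. That much rests on the text alone and needs no assumption.

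The effect on the data is unknown. The correlations depend entirely on the assumed lognormal shape and on error rates that no document supplies, so they show a range and are not an estimate. The direction is clearer than the size, because any such error moves long walkers to the bottom of the scale. Severity is minor: the unit is stated twice elsewhere in the item, and many bad records could be flagged afterwards, although the true values would be lost.

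**What to change.** Restate the example in the recorded unit, for instance: if you usually walk for 240 minutes on one day and 120 minutes on the other, enter the average, 180. This changes one line of help text and takes nothing away from the item.

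Optionally, add a soft confirmation when WP1A is 1 to 9 and WP1 is at least 1 day. The upper bound should be 9 and no higher, because entries of 10 to 12 minutes agree with WP1's own 10-minute threshold. It should ask for confirmation and not block the entry: someone who walks on one day a week and averages over all seven could truthfully report a figure below 10. The cost is one extra prompt for a few participants.

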Achieving a sample that is reflective of the UK population is an overarching aim of the Our Future Health programme for both ethical and scientific reasons. Ethically, it is important that we make substantial efforts to make participation in Our Future Health equitable and accessible to people regardless of their socioeconomic position, disability, physical health, mental health, sex, age, and ethnicity. Scientifically, it is important that the participants in Our Future Health are sufficiently diverse to facilitate a range of discovery and translational research the resource is intended to support. Related to this, the concept of “representativeness” has been debated at length in the

epidemiologic literature^{26,27}. We recognise that our participant sample is unlikely to be fully representative of the UK population in a large range of demographics and risk factors that extend beyond those shown in Table 1. However, the important aspects of representativeness and selection biases are specific to any hypothesis being tested and the external population to which an inference is to be made²⁸. By ensuring we recruit a diverse population, we will provide a resource that is amenable to a large range of hypotheses and potential inferences to improve the health of the UK population.

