Count the number of days in a week that you do vigorous physical activities for at least 10 minutes continuously at a time.

Remember to include activities that you do for work, leisure, travel and around the house.

[WP3A (UKB)]

Thinking about the last 4 weeks, how many minutes did you usually spend doing vigorous activities on a typical DAY?

Enter INTEGER

[Require $\geq 0, \leq 1440$

Units: minutes]

OR

-1 Do not know

OR

-2 Unable to walk -> **GO TO WP4AA**

OR

-3 Prefer not to answer

If the time you usually spend doing vigorous physical activity on each day of the week varies a lot, give an average of the time you spend doing vigorous physical activity.

[WP4 (UKB)]

How would you describe your usual walking pace?

SELECT one of 5 from

1 Slow pace

2 Steady average pace

3 Brisk pace

-7 None of the above

-3 Prefer not to answer

Slow pace is defined as less than 3 miles per hour. Steady average pace is defined as between 3-4 miles per hour. Fast pace is defined as more than 4 miles per hour.

[WP4A (UKB)]

At home, during the last 4 weeks, about how many times a DAY do you climb a flight of stairs? (approx 10 steps)

SELECT one of 8 from

- 0 None
- 1 1-5 times a day
- 2 6-10 times a day
- 3 11-15 times a day
- 4 16-20 times a day
- 5 More than 20 times a day
- 1 Do not know
- 3 Prefer not to answer

If you are unsure, please provide an estimate or select 'Do not know'.

[WP4AA (UKB)]

In the last 4 weeks, which forms of transport have you used most often to get about?
Not including travel to and from work; you can select more than one answer

TOGGLE of 6 choices

[Require ≥1 choices]

- 1 Car/motor vehicle
- 2 Walk
- 3 Public transport
- 4 Cycle
- 7 None of the above **[EXCLUSIVE]**
- 3 Prefer not to answer **[EXCLUSIVE]**

Remember not to include journeys to and from work.

[WP4B1 (UKB)]

In the last 4 weeks did you spend any time doing the following?
(You can select more than one answer)

TOGGLE of 7 choices

[Require ≥1 choices]

- 1 Walking for pleasure (not as a means of transport)
- 2 Other exercises (e.g., swimming, cycling, keep fit, bowling)
- 3 Strenuous sports
- 4 Light DIY (e.g., DIY that does not require a lot of physical effort)
- 5 Heavy DIY (e.g., DIY that requires a lot of physical effort)
- 7 None of the above **[EXCLUSIVE]** -> **GO TO WP11**
- 3 Prefer not to answer **[EXCLUSIVE]** -> **GO TO WP11**

- ➔ **If ANSWER = 1 GO TO WP4C1 (UKB)**
- ➔ **If ANSWER = 2 GO TO WP4C2 (UKB)**
- ➔ **If ANSWER = 3 GO TO WP4C3 (UKB)**

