Do you have any physical or mental health conditions or illnesses lasting or expected to last 12 months or more?

SELECT one of 4 from

- 1 Yes
- 0 No **-> GO TO H4B**
- 1 Do not know
- 3 Prefer not to answer

[H4A (UKB)]

Do you receive any of the following? (You can select more than one answer)

TOGGLE of 6 choices

[Require ≥1 choices]

- 1 Attendance allowance
- 2 Personal independence payment (previously disability living allowance)
- 3 Blue badge
- 7 None of the above **[EXCLUSIVE]**
- 1 Do not know **[EXCLUSIVE]**
- 3 Prefer not to answer **[EXCLUSIVE]**

Only select a response if you personally receive the benefit. Do not include if your spouse or someone in your household receives one of these benefits.

[H4B (UKB)]

Do you use private healthcare?

SELECT one of 6 from

- 1 Yes, all of the time
- 2 Yes, most of the time
- 3 Yes, sometimes
- 4 No, never
- 1 Do not know
- 3 Prefer not to answer

If you have access to private healthcare but always use the NHS, select No, never.

[COVID (WT Q)]

Do you think that you have or have had COVID-19?

- 1 Yes, confirmed by a positive test
- 2 Yes, suspected by a doctor but not tested
- 3 Yes, my own suspicions
- 4 No
- 1 Do not know
- 3 Prefer not to answer

[Y6AB (UKB)]

Do you wear sun protection (e.g., sunscreen lotion, hat) when you spend time outdoors in the summer?

SELECT one of 7 from

- 1 Never/rarely
- 2 Sometimes
- 3 Most of the time
- 4 Always
- 5 Do not go out in sunshine
- 1 Do not know
- 3 Prefer not to answer

If you are unsure, please provide an estimate or select 'Do not know'.

[H7C (UKB)]

Have you had any of the following in the past year?

(You can select more than one answer)

TOGGLE of 8 choices

[Require ≥1 choices]

- 1 Mouth ulcers
- 2 Painful gums
- 3 Bleeding gums
- 4 Loose teeth
- 5 Toothache
- 6 Dentures
- 7 None of the above **[EXCLUSIVE]**
- 3 Prefer not to answer **[EXCLUSIVE]**

[H8 (UKB)]

In the last year have you had any falls?

SELECT one of 4 from

- 1 No falls
- 2 Only one fall
- 3 More than one fall
- 3 Prefer not to answer

Do not include falls while playing sport or exercising.

[H9 (UKB)]

Compared with one year ago, has your weight changed?

SELECT one of 5 from

- 0 No - weigh about the same
- 2 Yes - gained weight
- 3 Yes - lost weight
- 1 Do not know
- 3 Prefer not to answer

[SY2 (UKB)]

In the last year have you ever had wheeze or whistling in the chest?

SELECT one of 4 from

- 1 Yes
- 0 No
- 1 Do not know
- 3 Prefer not to answer

→ IF WP1 = -2 GO TO SY4I

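### Baseline questionnaire: WP2A and WP3A accept inability to walk in place of minutes of non-walking activity, and the only skip past walking pace and stairs hangs on that answer

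*Protocol*

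**What the plan says.** All items are in the Protocol, Appendix E.

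- **WP1** (Section 3, days of walking) records inability to walk as code -2 and routes it "2 Unable to walk -> GO TO WP2". This skips only WP1A (walking minutes).
- **WP1A** offers the same code, with no skip attached.
- **WP2** asks on how many days the respondent did "10 minutes or more of moderate physical activities like carrying light loads, cycling at normal pace? (Do not include walking"). It has no inability-to-walk code.
- **WP2A** asks "how many minutes did you usually spend doing moderate activities on a typical DAY". The answer is a number from 0 to 1440, or -1, -2 (unable to walk) or -3. Code -2 has no skip here.
- **WP3** asks for days of vigorous activity, explained as follows: "These are activities that make you sweat or breathe hard such as fast cycling, aerobics, heavy lifting". It has no inability-to-walk code.
- **WP3A** asks for vigorous minutes in the same format as WP2A, but here code -2 reads "2 Unable to walk -> GO TO WP4AA". That jump passes over WP4 (usual walking pace) and WP4A (flights of stairs at home).
- **Section 5**, after SY2, has the rule "IF WP1 = -2 GO TO SY4I", which takes non-walkers past SY3 (breathlessness when walking) and SY4 (leg pain on walking).

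**The concern.** There are two faults, and they interact. First, WP2A and WP3A accept an answer to a different question. Being unable to walk is not an amount of cycling, lifting or aerobics, and WP1 has already recorded it. Second, the skip meant to spare non-walkers the pace and stairs items is attached to WP3A and not to WP1. The respondent can use it only by giving up the vigorous minutes.

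What is at stake is duration of activity in people with severe mobility limitation, some of whom exercise by other means. The introduction to Section 3 of the questionnaire says these items are there to relate exercise to general health and to specific organs and diseases. Protocol section 2.4 lists recent physical activity among the exposures that medical records capture poorly or not at all, so linkage is unlikely to fill the gap. Section 3.7 builds the short questionnaire from items already approved, so the fault could carry over if these items are chosen.

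**Working it through.** The plan gives no figure on this point, so the check is a trace of the printed routing from WP1 to WP4AA for a respondent with WP1 = -2, by type of answer at WP3A.

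| Answer at WP3A | Vigorous minutes recorded? | WP4 and WP4A skipped? |
|---|---|---|
| A number, 0 to 1440 | Yes | No |
| -2 (unable to walk) | No | Yes |
| -1 or -3 | No | No |

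No row has yes in both columns. Under the printed rules, a non-walker cannot both record vigorous minutes and skip the two walking items.

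Three further checks follow from the same text.

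1. **WP2A.** Code -2 replaces the moderate minutes and changes no routing. It costs a measurement and serves no purpose in the flow.
2. **The converse case.** A respondent who gave 0 to 7 days at WP1 can still choose -2 at WP3A. That contradicts WP1 and skips WP4 and WP4A for someone who walks.
3. **Comparison with Section 5.** To skip SY3 and SY4, the questionnaire tests WP1 = -2 directly. The same filter was available for WP4 and WP4A and was not used.

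**What is lost when -2 is entered.** Activity volume per week is days × minutes per day. Days come from WP2 and WP3 and are kept.

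- With 0 days, the product is 0 whatever the minutes, so nothing is lost.
- With 1 to 7 days, the product cannot be formed and the missing number cannot be reconstructed.

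**How many.** The documents give no prevalence of inability to walk. Write the number losing minutes as 5,000,000 × p × q × r, where p is the share unable to walk, q the share of those who enter -2 at WP2A or WP3A, and r the share of those with at least one active day on the matching item. If p is assumed to be 0.5% to 2%:

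- 5,000,000 × 0.005 = 25,000
- 5,000,000 × 0.02 = 100,000

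These are people exposed to the fault under an assumed p. Nothing in the documents bounds q or r below 1, so the number losing data lies somewhere between zero and that ceiling.

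**The case against.** Several stronger conclusions are tempting, and the documents do not support them.

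- **A reader might infer that -2 cannot be told from no activity, so that activity is biased downwards.** Both items allow a numeric 0, and -2 is a separate reserved code. An entry of three days with -2 is visibly different from zero days. The result is coded missing data. Downward bias would need an analyst to recode -2 to 0, and nothing in the Protocol says so.
- **A reader might infer that non-walkers lose their activity data.** Only minutes are at risk. Days at WP2 and WP3 are asked of everyone, and the jump to WP4AA lands before WP4B1 to WP4E5, which collect frequency and duration of other exercise, strenuous sport and DIY. These are a partial substitute only: their durations are banded, whereas the help text for WP2 and WP3 also brings in activity for work, travel and the home.
- **A reader might infer that the pace and stairs answers would be meaningless.** WP4 has a none-of-the-above option and WP4A a zero option, which is a true answer for someone who climbs no stairs. Since WP1 = -2 stays in the data, these answers can be set aside at analysis.
- **A reader might take 25,000 to 100,000 as a count of people losing data.** It is an assumed ceiling on those exposed.
- **A reader might cite section 2.3.1**, which wants participation to be "equitable and accessible to people regardless of their socioeconomic position, disability, physical health, mental health, sex, age, and ethnicity". That sentence concerns access to the programme, not questionnaire routing, and does not establish the fault.

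It can also be said that -2 is optional and a non-walker may simply type the minutes. That is so, and the cost is then two irrelevant but answerable items.

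These objections reduce the size of the problem. They do not remove it: the code is still offered where it answers nothing, the only skip is still tied to it, and minutes not entered cannot be recovered.

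**Conclusion.** The point stands as a routing and response-coding fault of limited reach. WP2A and WP3A should not offer inability to walk in place of minutes of non-walking activity, and the skip past WP4 and WP4A should not depend on that answer. As printed, a respondent with WP1 = -2 cannot both report vigorous minutes and skip the walking items, and each -2 at WP2A or WP3A leaves those minutes missing for good.

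The routing conclusion follows from the printed text and needs no assumption. The size is unknown: at most, those unable to walk who enter -2 and report at least one active day. Any figure for the share unable to walk is an assumption. The documents support selective missingness of minutes in this group, but not a demonstrated bias in activity level. It is worth correcting because the repair is nearly free and analysis cannot make good the loss.

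**What to change.** 1. Delete the inability-to-walk code (-2) from WP2A and WP3A.
2. After WP3A, insert: IF WP1 = -2 OR WP1A = -2 GO TO WP4AA.

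The WP1A condition is needed. Someone who answers 0, -1 or -3 at WP1 and then -2 at WP1A would not be caught by a test on WP1 alone, and step 1 removes the only skip that person could otherwise use.

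Under the new rule, a non-walker identified at WP1 or WP1A goes to WP4AA whatever is entered at WP3A, so a number there is kept and the walking items are skipped. A walker can no longer contradict WP1 by choosing -2 at WP3A. The rule follows the WP1 test already used after SY2; adding WP1A = -2 to that Section 5 rule as well would make the two identical.

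The cost is two response codes removed and one routing line replaced, with no added question. It is best done before large-scale recruitment and before items are chosen for the short questionnaire.
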